**1 \* Describe the purpose, specific aims, or objectives of this research. State the hypothesis to be tested:**

The purpose of this study is to develop and pilot test a novel App, in tablet-based form, to engage Veterans and providers in developing personalized, pro-active C-MEPPS for chronic low back pain. Our vision is an appealing user interface that increases Veteran access to self-management strategies, reliable information, and improved rehabilitative outcomes. The goal is to reduce pain impact and increase functional outcomes. This SPIRE effort will build and pilot test a web-based application empowering Veterans to overcome cLBP with a coordinated multidimensional evidence-based plan for pain self-management created by the Veteran. The specific aims of this project are aligned with primary Veterans Health Administration (VHA) strategic objectives, especially Strategy 1.1.2: "VA focuses on outcomes to tailor Veteran choice"; and: "Online navigator tools/information empowers Veterans to make decisions". This project responds to Rehabilitation Research and Development priorities: "Non-pharmacological activity-based interventions for chronic pain impacting outcomes that may include pain reduction... and QoL." Our secondary goal is to provide primary care and specialty services at VHA a novel, innovative, technologically appropriate, informative, and readily available tool in the fight against debility and poor health in Veterans with chronic low back pain.

Specific Aims:

- 1) To develop and pilot test a web-based application for Veterans, including women Veterans and older Veterans, applying User-Centered Design principles, empowering Veterans to build and use coordinated multidimensional evidence-based plans for pain self-management, aligned with each Veteran's preferences, interests, and strengths.
- 2) To promote behavior change targeting rehabilitative outcomes by identifying potential barriers to App use, e.g., usability and use, and by acquiring pilot data regarding future direction rehabilitative outcomes, including objective measures, e.g., physical activity, sleep duration, and patient-reported outcomes such as pain interference and improved quality of life.

**2 \* Discuss the research design including but not limited to such issues as: probability of group assignment, potential for subject to be randomized to placebo group, use of control subjects, etc.:**

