- o 1st follow up visit: the study subject will be introduced to the tablet App and instructed in use, all questions will be answered. The study subject will complete brief questionnaires pertaining to pain, sleep, quality of life, prior App experience, and pain interference. The study subject will be fitted with an actigraph and instructed in the use of the device.

- o 2nd followup phone call: The study subject will be contact by phone one week after the initial visit. Coaching on App use and troubleshoot of App and actigraph use will be provided. Brief pain and pain interference questionnaires will be administered.

- o 3rd followup phone call: The study subject will be contact by phone one week after the initial visit. Coaching on App use and troubleshoot of App and actigraph use will be provided. Brief pain and pain interference questionnaires will be administered.

- o 4th followup phone call: The study subject will be contact by phone one week after the initial visit. Coaching on App use and troubleshoot of App and actigraph use will be provided. Brief pain and pain interference questionnaires will be administered.

- o Final visit: the study subject will be introduced to the tablet App and instructed in use, all questions will be answered. The study subject will complete brief questionnaires pertaining to pain, sleep, quality of life, prior App experience, and pain interference. The study subject will be fitted with an actigraph and instructed in the use of the device.

- o Final follow up phone call: The subject will be briefly interviewed two weeks after final visit for final thoughts about the App use experience and any plans to change behaviors as a result of using the App for activity planning.

We will examine pilot data on usability, App use, and behavior change, and assess barriers to implementing changes planned by the Veteran through the App (failure mode analysis). The vision is that this will lead to future research on rehabilitation-oriented outcomes such as: functional measures, QoL, and pain.

Actigraph is a widely used activity meter, that non-invasively assesses the physical activity of the wearer. It is non-painful and non-invasive. It can be put in place and taken off by the study participant at will. As noted by the manufacturer: "ActiGraph is ISO-13485:2016 certified, and our activity monitors are FDA 510(k) cleared Class II medical devices in the U.S. and adhere to regulatory standards worldwide."

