- o Five Veterans from Empowering Veterans Program at the Baltimore-Loch Raven VA; (Site: Loch Raven VA)
- o Five female Veterans from the Women's health clinic; (Sites: Baltimore VAMHCS and Fort Meade VA)

Our pre-pilot objective is to reach two groups of Veterans: 1) 5 Veterans completing the EVP (Empower Veterans Program) and 2) 5 Veterans attending the Women's Health Clinic, in collaboration with [name], Director of Women's Health for VAMHCS. This will provide important feedback for the experience of two different groups: the first group is experienced with non-pharmacological, values-based, approaches to pain management including CBT, ACT, MBSR, and others. The Women's Health Clinic group may not have had formal exposure to non-pharmacological pain management and may require additional information or resources to attain maximal benefit from C-MEPPS. The goal is an App that is useful to the broadest number of Veterans. We will include at least 4 older Veterans among the 10 recruited so the App can be developed with input from older Veterans accessing whole-health integrative approaches to pain self-management.

Phase 3: Veteran Formal pilot testing group

- Multiple visits, phone interviews, and activity monitoring. Once feedback from the pre-pilot group is obtained and further modifications incorporated into READY-GO Pain, the App will be tested with a pilot group.
- 20 Veterans with cLBP a balance of middle-aged and older male and female veterans.
- The study procedures will include:
  - o Recruitment: the study will be introduced to potential study subjects by the PI, study investigators, colleagues, or the study coordinator
  - o Consent: the study will be described in detail to the potential study subjects by PI, study investigators, or the study coordinator. If the study subject agrees to participation, they will be given a pain diary to bring back at the time of the initial visit in 2 weeks time.
  - o Initial visit: the study subject will be introduced to the tablet App and instructed in use, all questions will be answered. The study subject will complete brief questionnaires pertaining to pain, sleep, quality of life, prior App experience, and pain interference. The study subject will be fitted with an actigraph and instructed in the use of the device. A 6-minute walk test will be completed. The Veteran will be given the tablet, loaded with the App, to take home and bring back at the follow-up and final visits.

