We will examine pilot data on usability, App use, and behavior change, and assess barriers to implementing changes planned by the Veteran through the App (failure mode analysis). The vision is that this will lead to future research on rehabilitation-oriented outcomes such as: functional measures, QoL, and pain.

Importantly, there will be no remote, network transmission of data using the tablet app during this study. Instead, completely de-identified information (i.e. data without any of the 18 HIPAA identifiers) will be entered and stored on the tablet for subsequent download when participants arrive at the VAMHCS facility for their planned in-person visits. Hence, there is no chance that VA sensitive information could be accidentally divulged by using the tablet in the manner detailed for this pilot study.

The data collected from participants with tablet APP is de-identified data. The tablet APP and tablet itself are VA approved so authorized connected to the VA network (WiFi and Wired).

2 \* Describe all procedures already being performed for diagnostic or treatment purposes (if not applicable to the study, enter "N/A"):

N/A

3 \* **Describe the duration of an individual participant's participation in the study:**  
The individual's participation in the study will not exceed 8 weeks.

4 \* **Describe the amount of time it will take to complete the entire study:**  
4 years

5 \* **Describe any additional participant requirements:**

Inclusion criteria include: Veterans receiving care at the VAMHCS, frequent or persistent low back pain (> 3 months), pain  $\geq 3$  on a 0-10 numeric rating scale, willing to participate in trial of non-pharmacological therapies for pain; ability to speak, read, and write as needed for study. Stable treatment.

ID: VIEW4E0280585B400  
Name: V2\_Study Procedures

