## Sample Size and Data Analysis

**If you uploaded a separate research protocol document in the 'Research Protocol' page, cite the applicable section and page numbers from that document in the answer boxes below.**

1 \* Provide the rationale and sample size calculations for the proposed target population:

This study is not powered to find statistically significant differences. Qualitative data interpretation will follow from a priori hypothesis development, in brief: specific design features, e.g. simple design, clear navigation, will improve Veteran experience. Quantitative aspects are not anticipated to attain statistical significance and will be descriptive.

2 \* Provide the plan for data analysis. Include in the description the types of comparisons that are planned (e.g., comparison of means, comparison of proportions, regressions, analysis of variance, etc.), which is the primary comparison/analysis, and how the analyses proposed will relate to the primary purposes of the study:

Both qualitative and quantitative methods of research analysis will be used. Data analysis will be performed utilizing a standard statistical analysis package, SAS and excel will be used to evaluate program development, implementation, qualitative instrument development, complex analytical methods, mixed methods research, and survey methodology.

Qualitatively, the current pilot study is designed to identify common barriers to App use.

Quantitatively, this study will obtain statistical information to guide the development of outcome measures for a Merit-level research proposal to determine the potential effectiveness of this multi-dimensional approach to pain self-management in an App.

ID: VIEW4E02806052800  
Name: v2\_Sample Size and Data Analysis

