## Behavioral Intervention

You indicated that this study involves psychosocial or behavioral interventions.

1 \* **Describe the intervention (duration, number of sessions, focus, etc.):**

Utilization of an Application to assist in care coordination. This will involve daily interaction with the tablet-based App during the 6 week period of the study. The interaction with the App itself could take a few minutes but during planning and education activities could take longer periods such as 30 minutes. The study participants will be coached in using the App. The intention is that the App will assist study participants in planning more healthful activities such as moderate daily exercise and improved sleep habits with an overarching goal of reducing pain intensity and interference.

The pilot phase study participants will meet with study staff multiple times during the study.

Phase 1: Veteran focus group

- Single occasion, focus group discussion: Up to five Veterans, recently graduated from the Empowering Veterans Program at the Baltimore-Loch Raven VA will meet during the first quarter of funding for this program. The group will be introduced to the prototype App on tablet computers. Using open semi-structured interviews, we will explore their use of non-pharmacological pain self-management strategies, with special attention to understanding use of language and how existing strategies link to labels and the values they associate with each. A total of five interface options will be included, to assess appeal, perceived navigability of these options, and input on design features and usability. Brief questionnaires will be completed at the end of the focus group session and compensation for participation will be distributed. (Site: Loch Raven VA). Duration 90 minutes, planning activities with an aim of reducing chronic pain intensity and interference will be discussed.

Phase 2: Veteran Pre-pilot group

- Single one-on-one interview: Using open semi-structured interviews, we will explore their use of non-pharmacological pain self-management strategies, with special attention to understanding use of language and how existing strategies link to labels and the values they associate with each. A total of five interface options will be presented to the interview subjects and rated for appeal, perceived navigability, design features, and usability. Validated questionnaires will be completed, see details below. Compensation for participation will be distributed.

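### Phase 3 first fits the actigraph at the visit that introduces the App, so objective activity has no pre-App wear, although a two-week lead-in already exists

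*Protocol*

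**What the plan says.** Study Procedures, item 1, sets out Phase 3 in order. At consent, participants receive a diary only: "they will be given a pain diary to bring back at the time of the initial visit in 2 weeks time". At the initial visit they are introduced to the App, complete questionnaires, do a 6-minute walk test and receive the device: "The study subject will be fitted with an actigraph and instructed in the use of the device". They leave with the App: "The Veteran will be given the tablet, loaded with the App, to take home". The final visit is 6 weeks later, when the devices are collected. Justification, Objective, & Research Design (item 2) and Behavioral Intervention also place the first fitting at the visit that introduces the App. Payment/Reimbursement Detail (item 3) gives App and actigraph the same 6 weeks of use.

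On what the device is for, Justification, Objective, & Research Design states: "Actigraph is a widely used activity meter, that non-invasively assesses the physical activity of the wearer". Aim 2 seeks pilot data on outcomes, "including objective measures, e.g., physical activity, sleep duration, and patient-reported outcomes such as pain interference". Behavioral Intervention says the App should help participants in "planning more healthful activities such as moderate daily exercise and improved sleep habits". Study Procedures adds: "We will examine pilot data on usability, App use, and behavior change". Observation (item 1) names actigraphy as one way individual behavior is assessed. Sample Size and Data Analysis says that "this study will obtain statistical information to guide the development of outcome measures for a Merit-level research proposal", and that the quantitative part is descriptive and not powered.

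**The concern.** Pain has a two-week diary before the App. Self-reported sleep, quality of life, pain interference and the 6-minute walk all have a value at the initial visit. Everyday activity recorded by the device, the objective counterpart of what the App is meant to change, has none. Phase 3 is a single group, so no control arm can stand in for the missing reference.

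Wear during App use will still show the level of activity, the spread between people, day-to-day variability, adherence and any trend over the 6 weeks. It cannot show change from before the App, or the SD of that change. Both would help in choosing and planning outcome measures for the later proposal. The timing of the fitting is a protocol procedure, and no later analysis can recover days that were never recorded.

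The same gap affects sleep duration only if the actigraph is its source. Aim 2 calls sleep duration objective, but the protocol describes the device only as measuring physical activity, so that link is an inference.

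**Working it through.** **Timeline**, in weeks from the initial visit (Study Procedures, item 1, Phase 3):

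| Event | Week |
|---|---|
| Consent, pain diary issued | -2 |
| App introduced, tablet taken home, actigraph first fitted | 0 |
| Final visit, devices collected | 6 |
| Final follow-up call | 8 |

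**The plan's own figure.** App and actigraph use = 6 - 0 = 6 weeks, which reproduces the 6 weeks in Payment/Reimbursement Detail.

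**Pre-App wear as planned.** First App exposure minus first fitting = 0 - 0 = 0 of 6 weeks.

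**Pre-App wear if fitted at consent.** 0 - (-2) = 2 weeks, with total wear 6 - (-2) = 8 weeks. Loan time rises by a factor of 8/6 = 1.33.

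**Recorded days.** The ceiling is 20 participants × 14 days = 280 participant-days. It needs daily wear by everyone, which the protocol does not specify. At half wear, or with the first lead-in week set aside because wearing the device may itself alter activity (both assumptions), it is 20 × 7 = 140.

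**Precision of the change quantities**, for n complete pairs. The protocol gives n = 20; n = 16 and n = 12 assume 20% and 40% loss.

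- 95% limits for the SD of change, as multiples of its estimate: √[(n-1)/χ²(0.975, n-1)] and √[(n-1)/χ²(0.025, n-1)].
- 95% half-width for the mean change, in SDs of change: t(0.975, n-1)/√n.

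| n | Lower SD factor | Upper SD factor | Half-width of mean change |
|---|---|---|---|
| 20 | √(19/32.852) = 0.76 | √(19/8.907) = 1.46 | 0.47 SD |
| 16 | √(15/27.488) = 0.74 | √(15/6.262) = 1.55 | 0.53 SD |
| 12 | √(11/21.920) = 0.71 | √(11/3.816) = 1.70 | 0.64 SD |

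**Length of participation.** Consent to last call = 2 + 6 + 2 = 10 weeks. Study Procedures, item 3, caps participation at 8 weeks, which fits only if the count starts at the initial visit (6 + 2 = 8). Earlier fitting does not lengthen the 10 weeks.

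**The case against.** The strongest reply is that the protocol does what it sets out to do. Phase 3 is about usability, App use and barriers. The quantitative part is declared descriptive, and no before/after actigraph comparison is promised. Behavior change is also covered by a self-report instrument and by the final call. If wear spans the 6 weeks, change from early to late App use and its SD can be estimated, along with between-person and day-to-day variability. All of that stands, and it is why this is an improvement and not an error.

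The gain is also modest. The SD limits depend only on n and would be the same for any outcome. A planning sample size proportional to the squared SD would be uncertain by factors of 19/32.852 = 0.58 to 19/8.907 = 2.13 at n = 20, and 11/21.920 = 0.50 to 11/3.816 = 2.88 at n = 12. First wear may itself alter activity, and with one group the effects of App, reactivity and time cannot be separated. This stands too, and limits the lead-in to description.

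Finally, the low cost is conditional. Informed Consent Process describes a face-to-face meeting in a private room, but Payment/Reimbursement Detail counts three visits, treats the initial visit as the first in-person session and pays nothing for a consent meeting. Recruitment spans four locations, and the number of devices is not stated. Wear instructions may sit in uploaded documents that are not at hand. These are real conditions on the change, but none of them supplies pre-App wear.

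What the objection does not answer is that early-to-late change during App use is a different quantity from change since before the App. The second cannot be obtained from the planned wear.

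**Conclusion.** The point holds as a worthwhile design improvement. All three descriptions of Phase 3 are consistent, and all leave actigraph activity with 0 of 6 weeks before the App. A two-week lead-in that could supply a reference is already scheduled.

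The loss is descriptive information, not power: the pre-App level, the mean change from it and the SD of that change. With the lead-in used, these would be estimated imprecisely (SD of change within 0.76 to 1.46 times its estimate, mean change to ±0.47 SD, at 20 complete pairs). Without it they cannot be estimated at all. The day counts assume daily wear, and the smaller-n figures assume 20% and 40% loss. The low cost assumes that consent is held in person two weeks before the initial visit, and is a judgement because device numbers are not given. Any resulting change should be described and not credited to the App.

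**What to change.** Issue and fit the actigraph at the in-person consent meeting, together with the pain diary, so that the existing lead-in yields up to 14 pre-App days. Keep the fitting step at the initial visit as a check and re-fit, as the 1st follow-up visit already does. Describe lead-in weeks 1 and 2 separately, so that any reactivity to first wearing the device can be seen.

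Costs:

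- Device loan rises from about 6 to about 8 weeks, which may need more devices if enrolment overlaps.
- Consent takes a few minutes longer, and participants wear the device for two more weeks.
- The first scheduled actigraph troubleshooting is the call one week after the initial visit, so lead-in wear is unsupported unless a call is added.
- No visit is added, provided consent is face to face two weeks ahead, as Study Procedures and Informed Consent Process together describe.

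The same amendment should reconcile the 8-week limit in Study Procedures, item 3, with the 10 weeks from consent to last call, and the visit count and payments in Payment/Reimbursement Detail with the consent meeting. The Phase 3 consent form should be brought into line. These passages need reconciling in any case, and device wear in the lead-in makes that period harder to leave out of the count.
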